Pharmacokinetic profile and dermatomal coverage of the erector spinae plane block - a comparison of bolus dosing and continuous infusion

Principal investigator: [name]., Assistant Professor, Virginia Commonwealth University Department of Anesthesiology

NCT number: not yet available

IRB approval date: March 6, 2019

Date of document: March 7, 2019

Introduction

Background

Muscle plane blocks are a fairly new regional anesthesia technique and are increasing in popularity. The most recent muscle plane block, termed the erector spinae plane (ESP) block, was developed to optimize pain control for thoracic surgery while minimizing the risks associated with paravertebral and epidural blocks. Numerous case reports have advocated for its use¹⁻⁴.

Significance of the research

In comparison to traditional neuraxial and peripheral nerve block approaches, a successful ESP block requires a higher volume of local anesthetic. Therefore, the optimal volume to produce analgesia from an ESP block may result in a plasma local anesthetic concentration that approaches toxic levels. Pharmacokinetic studies have been performed with muscle plane blocks, such as the quadratus lumborum block and transversus abdominus plane block^{5,6}; however, the pharmacokinetic profile of the ESP block has not yet been measured or studied. This study will demonstrate how quickly and closely toxic levels are reached when a routine dose of ropivacaine is given for the ESP block and will also assess for areas of numbness created by the ESP block when routine doses are administered.

Specific aims of the project

- Create plasma ropivacaine concentration-time curves after performance of an ESP block via bolus and continuous infusion into the ESP compartment. The concentration-time curves will include the peak serum concentration of ropivacaine (C_{max}) and the time required to reach maximum plasma concentration (T_{max}).
- Determine the dermatomal distribution and duration of analgesia created when ESP block is performed via ropivacaine bolus versus continuous ropivacaine infusion.

Methods

Study design

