The ESP block procedure - participant consent will be performed on the day of surgery by one of the research investigators in the pre-operative surgical unit (PSU). Randomization is not required because all participants will be undergoing the same protocol. All participants will also be undergoing cardiac surgery by the same surgeon. Routine care will be performed for the placement of the ESP block and is described as follows: the ESP block will be performed by the acute pain service, which will have members that are not involved with the research. Adequate block placement will be confirmed by one of the investigators via ultrasound images that are captured during the procedure. The participant, who is already in a patient gown with an intravenous line (IV) in place, will be positioned sitting on the side of the patient bed. Vital sign monitoring with pulse oximetry and blood pressure cuff will be connected. The participant will be given intravenous midazolam to reduce anxiety and enhance comfort during the ESP block procedure. Full aseptic precautions will be taken with personal protective equipment and bactericidal preparation with chlorhexidine. An ultrasound probe will be placed lateral to the patient's upper back and the ideal location of medication injection will be identified on an ultrasound image (which is superficial to the transverse processes of the thoracic vertebral bodies and deep to the erector spinae muscle). The skin will be made numb with lidocaine prior to insertion of a larger needle (Tuohy needle); the proceduralist will direct the Tuohy needle to the desired target under ultrasound guidance and 25 cc 0.25% ropivacaine will be delivered through that needle. A continuous nerve catheter will then be inserted through the Tuohy needle to allow for continuous delivery of medication if desired. The Tuohy needle will be removed, and the nerve catheter will be secured in place with adhesive dressing. Cardiac surgery will require bilateral (left and right) nerve catheter placement, and therefore, upon completion of one side, the ESP block will be performed on the other side. The estimated time needed for a bilateral ESP block procedure is 30 minutes. After the completion of the ESP block procedure, the participant will undergo their planned cardiac surgery procedure, which typically takes many hours.

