Initiation of continuous nerve catheter infusions (alteration of standard care) - this component of care will be different than routine care. Nerve catheter infusions are typically initiated at the end of the surgical procedure at a concentration and rate of 0.2% ropivacaine at 8-10 cc/hr.

The study protocol will direct the nerve catheter infusions to run at 1 cc/hr; this rate will allow the nerve catheters to remain open and patent but will not significantly interrupt or alter the quality of the research data collection. The operating room team and ICU staff will be notified about the patient's participation in the study and will have information available regarding the alterations from routine practice that would be required for this study.

Research protocol, part 1 - the research protocol and data collection will begin on the afternoon of post-operative day 1 (the day after surgery) in the cardiac surgery intensive care unit (CSICU). Typically, cardiac surgery patients will be sedated and have a breathing tube in place until the morning of post-operative day 1. This delayed timing of the study will allow the participant to stabilize after removal of the breathing tube. Although written consent has already been obtained, a research investigator will obtain a verbal reaffirmation from the participant and update the CSICU team before proceeding.

Per routine, the participant will have vital sign monitors connected and have an arterial line in place that will allow for collection of blood samples for laboratory testing. The nerve catheter infusions will be suspended and the research protocol will begin in the CSICU as follows: the investigator will administer 25 cc 0.25% ropivacaine through each nerve catheter (totaling 50 cc 0.25% ropivacaine) and record the time of administration on a data collection sheet. Either the investigator or study assistant will collect arterial blood samples at the following intervals after the medication bolus: 10 minutes, 15 minutes, 30 minutes, 45 minutes, 60 minutes, 90 minutes, 2 hours, and 4 hours. The blood samples will be labeled with a patient ID sticker and will also contain the study ID number and the time interval that corresponds with the blood sample. The samples will be stored in a designated ice cooler that will be delivered to the clinical laboratory.

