During this first portion of sample collection, the secondary outcome of dermatomal analgesia and duration will be assessed. At the 60-minute interval, a study investigator will test areas of numbness performing a pinprick test and using a dermatomal map to mark the areas of numbness. For the pinprick test, the investigator will use a pointed object that is sharp enough to elicit a sharp sensation but blunt enough that it does not cause skin damage; the participant will be asked to provide comparison of the sensation of the pointed object when it is applied to an area that is not expected to be numb (like the palm) versus an area that is expected to be numb (like the chest and thorax). At the 90-minute, 2 hour, and 4 hour intervals, the participant will be asked if the numbness from the nerve block has gone away. If the resolution of numbness occurs between the time intervals, the participant will be asked to look at the clock and remember the time at which the difference was felt. It is expected that at the 4-hour interval, the serum ropivacaine level will be approaching or have reached the baseline level before the bolus was given.

Research protocol, part 2 - at the 4-hour interval (4 hours after the initial bolus), both nerve catheter infusions will be resumed at a concentration and rate of 0.2% ropivacaine at 10 cc/hr. Either the investigator or study assistant will collect arterial blood samples at the following intervals after the start of the infusion: 60 minutes, 2 hours, 4 hours, 8 hours, 12 hours, 24

hours. Dermatomal analgesia assessment will be performed by one of the research investigators at the 24-hour mark. After this assessment, the research protocol will be considered complete and routine care by the CSICU and acute pain service will resume. The researchers will collaborate with the health care teams during the study protocol if this becomes necessary to maintain patient safety and comfort.

The collected blood samples are viable for one week if they are refrigerated and one month if they are frozen. Free and total ropivacaine levels will be determined for each sample by the clinical laboratory and this information will be distributed to the research investigators in a way that protects patient health information and will be recorded securely onto a data collection sheet. The data for this sheet can then be used for statistical analysis and creation of a pharmacokinetic profile for the ESP block (both bolus and infusion curves).

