Data analysis

A two-sample Kolmogorov-Smirnov test will be used to determine the difference between the distributions of the bolus arm and the infusion arm. T_{max} and C_{max} of the two arms will be analyzed with an unpaired t-test. A logrank test will be used to assess the difference between the duration of analgesia created by the bolus arm and the infusion arm.

Institutional board approval

The protocol has been approved by Virginia Commonwealth University Institutional Review Board (Study ID HM20014803).

Literature cited

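### The between-regimen t-test of T_max is a foregone conclusion set by input type and sampling times, and the C_max test is unpaired although each participant supplies both values

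*Combined protocol and SAP*

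**What the plan says.** Aim 1 (Specific aims of the project) promises concentration-time curves for bolus and infusion, each with C_max and T_max. T_max has one definition for both, the time taken to reach the maximum concentration. Data analysis adds: "T_{max} and C_{max} of the two arms will be analyzed with an unpaired t-test".

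The arms are not separate groups. Under Description of procedures: "Randomization is not required because all participants will be undergoing the same protocol". Each participant goes through two phases.

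- **Bolus (Research protocol, part 1):** "the investigator will administer 25 cc 0.25% ropivacaine through each nerve catheter (totaling 50 cc 0.25% ropivacaine", sampled "after the medication bolus: 10 minutes, 15 minutes, 30 minutes, 45 minutes, 60 minutes, 90 minutes, 2 hours, and 4 hours". By the end of this phase it is expected that "the serum ropivacaine level will be approaching or have reached the baseline level before the bolus was given".
- **Infusion (Research protocol, part 2):** at that 4-hour point "both nerve catheter infusions will be resumed at a concentration and rate of 0.2% ropivacaine at 10 cc/hr", sampled "after the start of the infusion: 60 minutes, 2 hours, 4 hours, 8 hours, 12 hours" and finally at 24 hours.

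The plan gives no hypothesis for T_max, no separate definition for an infusion, no rule for a maximum at the last sample, and no sample size or significance level.

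**The concern.** One label is applied to two different quantities. After a single dose the level rises, peaks and falls, so the time of the maximum describes a feature of the curve. Under constant input the level climbs towards a plateau, and the time of the highest reading depends on when samples were drawn and, once the plateau is reached, on measurement error.

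The sampling grids widen the gap. Four of the eight bolus times (10 to 45 min) come before the first infusion sample. Three of the six infusion times (8, 12 and 24 h) come after the last bolus sample. Only 1, 2 and 4 h are shared.

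At stake is how the result will be read. A small p-value for T_max invites a statement about how quickly the drug is taken up under each regimen, and the test cannot support one. In the same sentence, C_max is to be analysed as if the two sets of values came from different people. That does affect the standard error of a comparison worth making.

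**Working it through.** **Figures to reproduce.** None. The documents give no sample size, power or expected T_max.

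**Inputs from the documents.** Bolus 50 mL × 2.5 mg/mL = 125 mg. Infusion 10 mL/h × 2 mg/mL = 20 mg/h if the stated rate is the total, or 2 × 20 = 40 mg/h if it is per catheter; both readings were run. Sampling times as stated.

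**Assumptions, none from the documents.** One compartment with first-order absorption; between-patient log-SD 0.4 (absorption) and 0.25 (elimination); lognormal residual CV 5%, 10% or 20%; bolus residue carried into the infusion phase; infusion T_max counted from infusion start; two-sided 0.05.

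**Step 1: shape of the curves.** With ka and ke equal to ln 2 divided by the absorption and elimination half-lives:

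- Bolus peak time: t* = ln(ka/ke) / (ka − ke).
- Infusion, as a fraction of plateau: F(t) = 1 − (ka·e^(−ke·t) − ke·e^(−ka·t)) / (ka − ke). Its slope, ka·ke·(e^(−ke·t) − e^(−ka·t)) / (ka − ke), is positive at every t > 0, so there is no interior peak.

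**Step 2: what the 4-hour expectation implies.** With absorption half-life 0.2 h, the 4-hour bolus level is 12% of peak at an elimination half-life of 1 h, 25% at 1.5 h, 36% at 2 h and 62% at 4 h. A level close to baseline by 4 h therefore points to a short half-life. At 1 h, ka = 3.466, ke = 0.693 and ka/(ka − ke) = 1.25, so F(8) ≈ 1 − 1.25 × 0.0039 = 0.995, and F(12) and F(24) round to 1.000. The three late samples differ by about 0.5%, far less than the assumed residual CV. At a half-life of 8 h, F is 0.487, 0.637 and 0.872 at 8, 12 and 24 h, so the level is still rising.

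**Step 3: where infusion T_max falls** (absorption half-life 0.2 h, 40 mg/h, CV 10%; between-patient log-SD 0.3 for both rates in this step):

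| Elimination half-life | 8 h | 12 h | 24 h |
|---|---|---|---|
| 1 h | 27% | 31% | 30% |
| 2 h | 21% | 34% | 43% |
| 4 h | 6% | 23% | 71% |
| 6 h | 2% | 13% | 86% |

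With no residual error it is 24 h in every simulated patient. At a 1 h half-life and CV 10%, mean infusion T_max is 9.1, 13.6 or 22.1 h if sampling ends at 12, 24 or 48 h.

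**Step 4: bolus T_max.** At absorption half-life 0.25 h, t* = ln 4 / (2.773 − 0.693) = 0.67 h when elimination half-life is 1 h, and ln 32 / (2.773 − 0.087) = 1.29 h when it is 8 h. On the protocol grid the simulated means (CV 10%) are 0.72 h and 1.42 h. Raising absorption half-life to 1 h with elimination at 1 h gives 1.44 h. Both processes matter about equally.

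**Step 5: the planned test.** Settings with a 4-hour level at or below 25% of peak (absorption half-life 0.25 or 0.5 h, elimination 1 h, three CVs, two rates; 12 settings):

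| Infusion uptake | n | Pooled t-test rejects |
|---|---|---|
| Equal to bolus | 3 | 63%–87% |
| Equal | 5 | 96%–100% |
| Equal | 6 | 99%–100% |
| Halved | 6 | 99.9%–100% |
| Doubled | 6 | 98%–100% |
| Any of the three | 10 | 100% |

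Over all 72 settings (elimination half-life up to 8 h, equal uptake) it rejects in 98%–100% at n = 6. A paired T_max test still rejects in 97%–100% at n = 6 over the 12 settings with equal uptake, so pairing does not rescue it. The rank correlation between a participant's two T_max values is 0.02 to 0.09.

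**Step 6: C_max.** The unpaired test takes the variance of a difference as s_b² + s_i² on 2n − 2 degrees of freedom. With both values from one person it is s_b² + s_i² − 2·r·s_b·s_i on n − 1. At n = 6 that is 10 against 5 degrees of freedom. With positive r the planned standard error is too large. The documents give no basis for r.

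**The case against.** **The difference in T_max is real, and no passage says the test measures uptake.** Both parts are right. In every simulated setting the true maxima do fall at different times, so the rejection rates are power. A reader might take them for false-positive rates, because uptake was set equal; that reading is wrong. What remains is that the answer is known before any sample is drawn, and that the plan gives no meaning for it.

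**Bolus T_max is not a pure measure of uptake.** This stands; step 4 shows that elimination moves it as much as absorption does. It is still the time of an actual peak, and it serves the protocol's question of "how quickly and closely toxic levels are reached when a routine dose of ropivacaine is given for the ESP block".

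**Infusion T_max need not be assay noise.** This stands too. A reader might infer that it is always a random pick among plateau readings. That holds only at short half-lives. At longer ones the value is fixed mainly by the 24 h stop. The 4-hour expectation favours the first case, but its wording is loose and its baseline follows a keep-open infusion, so it does not settle the matter. Neither case yields an informative T_max.

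**The percentages are assumed.** They are. At n = 3 rejection is not assured, and it is only 27%–43% with the Welch form. The direction does not depend on the particular half-lives, though it does assume linear kinetics and a bolus residue below the infusion plateau.

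**C_max is a separate defect.** Agreed. It sits in the same sentence and is settled by the same edit, but it adds no weight to the T_max argument.

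**Conclusion.** The point holds. Comparing T_max between regimens sets a bolus peak time of at most 4 h against an infusion value governed by the sampling schedule. From about 5 or 6 participants the test is close to certain to reject whatever the relative uptake (about 98%–100% at n = 6). These figures rest on an assumed one-compartment model, variability, assay error and a 0.05 level. The number of participants is not stated.

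The documents do not support a stronger claim that the test is invalid in the sense of rejecting a true null, or that the trial's conclusions are at risk. T_max is one of four planned comparisons, no stated decision depends on it, and the collected data are unaffected. The unpaired C_max test is wrong as written, because the same-participant structure is explicit in the protocol. Both should be corrected before analysis.

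**What to change.** In Data analysis:

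1. Remove T_max from the between-regimen test.
2. Report bolus T_max as median and range.
3. For the infusion, report the levels at 8, 12 and 24 h, and call the maximum *highest concentration observed within 24 h*.
4. Compare C_max within participants with a paired analysis on the log scale, giving the ratio and its confidence interval. State three limits: the bolus always comes first; bolus residue carries over into the infusion phase; and the maximum of several noisy plateau samples is biased upward. In the model (half-lives 0.25 h and 1 h, 40 mg/h) the infusion maximum is too high by 4%, 9% and 21% at CV 5%, 10% and 20%. The bias in the infusion-to-bolus ratio is smaller (from 0.75 to at most 0.79), because the bolus maximum is inflated as well.

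In Specific aims, reword Aim 1 so that T_max is promised for the bolus curve only, with the 24-hour maximum and late levels for the infusion.

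The cost is one uninformative p-value and a minor wording amendment to a protocol that already has board approval. No sample, visit or procedure changes.

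### C_max is to be compared by a t-test with no log transformation stated, and no interval or upper-percentile summary is planned despite the toxicity aim

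*Combined protocol and SAP*

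**What the plan says.** The comparison of peak levels is planned in one sentence of the Data analysis section: "T_{max} and C_{max} of the two arms will be analyzed with an unpaired t-test". The scale is not written. A t-test named without a transformation is naturally read as a comparison of arithmetic means.

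The only other comparison of concentrations is in the same section: "A two-sample Kolmogorov-Smirnov test will be used to determine the difference between the distributions of the bolus arm and the infusion arm". The section names tests only. It contains no confidence interval, SD summary, reference range, percentile or tolerance limit for C_max.

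Significance of the research gives the purpose: "This study will demonstrate how quickly and closely toxic levels are reached when a routine dose of ropivacaine is given for the ESP block". No toxic threshold is stated.

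Under Description of procedures, the bolus volume and the infusion rate are the same for every participant, and no weight adjustment is stated. The two regimens are given to the same people. The plan says "Randomization is not required because all participants will be undergoing the same protocol", and in part 2 of the research protocol, "at the 4-hour interval (4 hours after the initial bolus), both nerve catheter infusions will be resumed". Two analytes are measured ("Free and total ropivacaine levels will be determined for each sample by the clinical laboratory"), and the analysis section does not say which one supplies C_max.

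**The concern.** C_max cannot be negative. When everyone receives the same amount of drug, differences in body size, absorption and clearance tend to act on the level as factors. That usually gives right skew and a spread that grows with the level. A t-test on untransformed values then lets a few high patients drive both the mean and the SD, and loses power against a proportional difference between regimens.

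The second part is an omission. How close patients come to toxic levels is a question about high individual values. The planned tests ask whether the two regimens differ in mean or in distribution; neither estimates how high a patient's peak may go.

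The scale question is separate from the unpaired test. It remains if the test is made paired, and in most of the settings examined it then matters more.

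**Working it through.** **Inputs.** The documents give no sample size, alpha, power, SD, CV, expected ratio or within-participant correlation, so there is no planned figure to reproduce. Assumed for illustration: log-normal C_max, the same CV in both phases, CV 40-70% (with 30% as a milder case), n = 10-20, infusion:bolus ratio 1.4, log-scale correlation 0.3-0.6, two-sided alpha 0.05.

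**Step 1: log-scale SD.** s = sqrt(ln(1 + CV²)).
- CV 40%: sqrt(ln 1.16) = 0.385
- CV 50%: sqrt(ln 1.25) = 0.472
- CV 70%: sqrt(ln 1.49) = 0.631

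**Step 2: power.** Pairs of log-normal values were simulated, 20,000 trials per setting, and t-tests on C_max and ln(C_max) were compared. Power is shown as raw v log; simulation error and rounding together can move an entry by about a point.

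| n, CV | Unpaired, corr. 0.6 | Paired, corr. 0.3 | Paired, corr. 0.6 |
|---|---|---|---|
| 10, 50% | 24% v 27% | 35% v 40% | 54% v 61% |
| 15, 50% | 42% v 46% | 53% v 59% | 75% v 82% |
| 15, 70% | 17% v 21% | 30% v 37% | 46% v 58% |

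At CV 40% and correlation 0.6, paired power is 73% v 78% (n = 10) and 91% v 94% (n = 15). Over the whole grid the loss is about 2-6 points unpaired and about 1-12 points paired. The small paired losses arise where power is already near its ceiling. At CV 30% the loss is about 0-3 points.

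**Step 3: type I error.** In a second set of simulations (n = 10, 20 and 30; CV 30%, 50% and 80%; correlation 0), the raw unpaired test rejected a true null in 3.9% to 5.3% of trials. At correlation 0.5 the unpaired test rejected in under 1% of trials on either scale. That is the effect of ignoring the pairing, not of the scale.

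**Step 4: upper range, if mean and SD were used to describe it.** For a log-normal variable, in multiples of the median:
- mean + k SD = sqrt(1 + CV²) × (1 + k CV)
- true percentile = exp(k s)

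| CV | Mean + 1.645 SD | True 95th | Short by | Mean + 1.96 SD | True 97.5th | Short by |
|---|---|---|---|---|---|---|
| 40% | 1.077 × 1.658 = 1.79 | 1.88 | 5% | 1.077 × 1.784 = 1.92 | 2.13 | 10% |
| 50% | 1.118 × 1.823 = 2.04 | 2.17 | 6% | 1.118 × 1.980 = 2.21 | 2.52 | 12% |
| 70% | 1.221 × 2.152 = 2.63 | 2.83 | 7% | 1.221 × 2.372 = 2.90 | 3.45 | 16% |

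**Step 5: intervals, if raw-scale ones were reported.** A 95% t-interval for one regimen's mean would lie wholly below the truth in about 5-9% of trials, against a nominal 2.5%. For the paired difference, where skew partly cancels, the figure is about 3-5%.

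**The case against.** Four things can be said for the plan.

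- **The scale is partly a choice.** Toxicity concerns absolute concentration, and a difference in arithmetic means is a legitimate target. The log analysis answers a different question. This stands: the change of estimand must be stated, and arithmetic summaries deserve a place. But the plan's comparison of means does not address the upper tail either.
- **The loss under the planned test is small.** This also stands. Pairing is the larger defect in the same sentence: at n = 10, CV 50% and correlation 0.6, pairing alone lifts raw-scale power from 24% to about 54%, whereas logging the unpaired test lifts it from 24% to 27%. Once the pairing is corrected, though, the scale is worth a further 7 points in that setting.
- **Every magnitude is assumed.** The documents contain no data on skew or CV. The direction is well founded for positive concentrations at a fixed dose; the size is not known.
- **The Kolmogorov-Smirnov comparison does not depend on scale.** True, since a log transformation leaves its statistic unchanged. But it gives neither an estimate of C_max nor an upper limit.

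A reader might go further and infer that the plan reports off-centre intervals and understates the upper range. The documents do not support that: the analysis section specifies no interval and no mean-and-SD range. The shortfalls in steps 4 and 5 would follow only if raw summaries were chosen at the reporting stage.

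**Conclusion.** The point holds as a cheap improvement. The plan states no log transformation for the t-test on C_max and plans no interval or upper-percentile summary, although closeness to toxic levels is a stated purpose.

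Under log-normality with the assumed inputs, the cost in power is modest for the test as planned and can reach about 12 points once the test is paired. At CV 30% it is close to negligible. The upper-range shortfall of about 5-7% at the 95th percentile (10-16% at the 97.5th) is conditional on reporting that the plan does not specify.

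It would be wrong to conclude that the raw scale produces false positives; the simulated type I error is near or below 5%. Confidence is high on what the plan states and omits, and moderate on size.

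**What to change.** Replace the C_max part of the Data analysis sentence with a statement along these lines:

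- ln(C_max) will be analysed using within-participant differences, because each participant supplies both values.
- The contrast will be the infusion:bolus geometric mean ratio with a 95% CI.
- For each phase, the geometric mean with a 95% CI and a back-transformed upper percentile, or an upper tolerance limit, will be reported.
- Arithmetic means and SDs in concentration units will be kept as descriptive summaries.

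The same text should say whether C_max refers to free ropivacaine, total ropivacaine or both.

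The cost is a sentence or two in the plan; no extra samples or data are needed. The downside is that the contrast becomes a ratio instead of a concentration difference, which the plan should state. With a small sample, the upper percentile or tolerance limit will be imprecise and will depend on the log-normal assumption, so the individual values should be shown with it. The change does not address the fixed order of the regimens, with the infusion starting 4 hours after the bolus; the ratio describes the regimens as given in that sequence.

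### The logrank test cannot compare duration of analgesia: numbness under infusion is checked once, at 24 h, so no infusion offset time is observed

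*Combined protocol and SAP*

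**What the plan says.** The second specific aim is to determine the distribution and duration of analgesia with a bolus versus a continuous infusion. The Data analysis section gives duration one analysis: "A logrank test will be used to assess the difference between the duration of analgesia created by the bolus arm and the infusion arm".

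The assessments are described under Description of procedures.

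- **Part 1 (bolus).** Duration belongs here: "During this first portion of sample collection, the secondary outcome of dermatomal analgesia and duration will be assessed". After pinprick mapping at 60 minutes, the follow-up is: "At the 90-minute, 2 hour, and 4 hour intervals, the participant will be asked if the numbness from the nerve block has gone away". Participants are asked to note the clock time if numbness resolves between these checks.
- **Part 2 (infusion).** At 4 h after the bolus, "both nerve catheter infusions will be resumed at a concentration and rate of 0.2% ropivacaine at 10 cc/hr". Blood is drawn "at the following intervals after the start of the infusion: 60 minutes, 2 hours, 4 hours, 8 hours, 12 hours, 24" hours. The only sensory check is: "Dermatomal analgesia assessment will be performed by one of the research investigators at the 24-hour mark". Then: "After this assessment, the research protocol will be considered complete and routine care by the CSICU and acute pain service will resume".

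No event, time origin or censoring rule is given for the logrank test. No stop of the infusion and no later numbness check is described. Every participant goes through both parts in the same order.

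**The concern.** A logrank test compares times to an event. Here the event must be loss of numbness, and the schedule yields such times only for the bolus. The infusion phase gives a single yes or no at 24 h. A yes is a record censored at 24 h. A no means that numbness was lost at an unknown hour or never appeared.

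The test will still run and return a p-value. If all participants are numb at 24 h, that p-value sets a bolus that wears off against an infusion that is not described as stopped. It would be reported as infusion analgesia lasting longer. If some are not numb, the analyst must assign them a time without a rule, and that choice can decide whether the result is significant.

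**Working it through.** **Inputs from the protocol.** Bolus follow-up ends at 4 h, when the infusion starts in the same participant. Infusion numbness is observed once, at 24 h. The plan states no sample size, event count or p-value for this test, so there is no figure to reproduce.

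**Assumptions.** n = 10 participants, each contributing one bolus and one infusion record; b bolus offsets by 4 h, untied and spread over 1.6 to 3.9 h, the rest censored at 4 h; k participants not numb at 24 h. The two phases are treated as independent, as the planned test does.

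**Step 1: formula.** At each event time let n_I and n_B be the numbers at risk under infusion and bolus, and d the number of events. For the infusion group:

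- E = Σ d·n_I/(n_I+n_B)
- V = Σ d·n_I·n_B/(n_I+n_B)² × (n_I+n_B−d)/(n_I+n_B−1)
- z = (O−E)/√V

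**Step 2: times after 4 h drop out.** After 4 h, n_B = 0. Each later infusion event adds 1 to O, n_I/n_I = 1 to E and 0 to V. So z does not change, whatever n is.

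**Step 3: example with b = 4, and no infusion event coded by 4 h.**

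- E = 10/20 + 10/19 + 10/18 + 10/17 = 2.170
- V = 0.2500 + 0.2493 + 0.2469 + 0.2422 = 0.988
- z = (0 − 2.170)/√0.988 = −2.18, p = 0.029

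If all 10 lose infusion numbness at 4.5 h, O = 10 and E = 12.170, so O − E is again −2.170 and p is again 0.029.

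**Step 4: results over b and coding.** Near zero means 0.01 h. Every result in the table leans towards infusion.

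| Infusion coding | b = 4 | b = 6 | b = 8 | b = 10 |
|---|---|---|---|---|
| All numb at 24 h, or any k coded after 4 h | 0.029 | 0.0040 | 0.00025 | 0.000003 |
| k = 1, near zero | 0.16 | 0.032 | 0.0035 | 0.0001 |
| k = 2, near zero | 0.43 | 0.13 | 0.022 | 0.0013 |
| k = 3, near zero | 0.81 | 0.33 | 0.085 | 0.009 |
| k = 3, at 2 h | 0.71 | 0.27 | 0.052 | 0.005 |

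With b = 3 and no infusion event coded by 4 h, p = 0.067. As a check on k = 3 near zero with b = 4: E = 3·10/20 + 7/17 + 7/16 + 7/15 + 7/14 = 3.316, V = 1.658, z = (3 − 3.316)/√1.658 = −0.25, p = 0.81.

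Coding at or before 4 h can therefore remove significance, but not when few participants are not numb and many boluses have worn off. A significant result favouring bolus under near-zero coding needs at least 8, 9, 9 or 10 of 10 not numb, for b = 4, 6, 8 or 10.

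**Step 5: other sample sizes.** For n = 8 and b = 3, 5, 6, the all-numb p-values are 0.063, 0.0085 and 0.0023; with k = 2 near zero they become 0.72, 0.24 and 0.11. For n = 20 and b = 8, 12, 16, they are 0.0017, 0.000033 and 0.0000001; with k = 6 near zero, 0.70, 0.15 and 0.011.

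**Step 6: false positives.** In a simulation, both phases had the same exponential duration distribution and every infusion record was placed at 24 h. At n = 10 the nominal 5% test rejected in 99%, 85% and 35% of 1,000 runs, for median durations of 2, 4 and 8 h.

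**The case against.** The strongest reply is that right-censoring is legitimate. A participant numb at 24 h is a valid censored record, and any logrank test with unequal follow-up uses only the time when both groups are at risk. If all are numb at 24 h and the boluses have worn off by 4 h, saying that numbness persisted longer under infusion is not false. That stands as far as it goes. But it assumes unbroken numbness from the start of infusion, including hours 0 to 4, which nobody checks. And it says only that an infusion not described as stopped outlasted a single bolus.

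It is also fair that the p-values rest on assumed counts and on untied offsets. With all bolus offsets tied at 4 h, the k = 3 near-zero values for 8 and 10 offsets are 0.18 and 0.047, not 0.085 and 0.009. The direction holds; the exact figures do not. The absence of infusion offset times depends on none of these assumptions.

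Duration is a secondary outcome, and the concentration-time, Cmax and Tmax data are untouched. That limits the damage but does not make the analysis valid. Treating two periods in the same participants as independent arms is a further fault, shared with the other planned tests and not needed for this conclusion. The clock-time instruction does not help, because it appears only in part 1 and is tied to the bolus checks.

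**Conclusion.** The concern holds, and the analysis is wrong as written and must be changed. By design the infusion phase yields no offset times, and the logrank statistic is decided by hours 0 to 4, when infusion numbness is not observed. Neither statement depends on n. How far the p-value misleads does depend on n, on the number of boluses worn off by 4 h and on the number not numb at 24 h, none of which the protocol gives. With 10 participants and 4 or more bolus offsets, the test is significant in favour of infusion whenever no infusion event is coded at or before 4 h, whatever happens later. With 2 participants not numb and coded near zero, significance is lost with 4 or 6 bolus offsets and kept with 8 or 10.

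**What to change.** **Option A: rewording, no new data.** Delete the between-regimen logrank test and reword the second aim so that it no longer promises a comparison of duration.

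- Report bolus duration by a Kaplan-Meier or interval-censored (Turnbull) estimate, censored at 4 h, with a 95% CI. State how a participant who is not numb at 60 minutes is handled.
- For the infusion, report the proportion numb and the number of blocked dermatomes at 24 h, each with a 95% CI.
- If a comparison is wanted, compare paired dermatome counts (60 minutes after bolus versus 24 h of infusion) with a Wilcoxon signed-rank test. Use the same mapping method at both times, and state the fixed order and possible carry-over from the bolus.

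The cost is a change to one analysis sentence and one aim of an IRB-approved protocol, with whatever amendment step that requires, and the loss of a p-value the data cannot support.

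**Option B: if a time-based comparison is to stay.** Also ask about numbness at the infusion blood draws at 60 minutes and 2, 4, 8 and 12 h. Define the event, time origin and censoring rule, including for participants still numb from the bolus when the infusion starts. Name a paired or interval-censored method in advance.

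The cost is five questions per participant at draws that already take place. Work starts "the research protocol and data collection will begin on the afternoon of post-operative day 1"; if the bolus falls between 12:00 and 18:00 (assumed), the infusion starts 4 h later, at 16:00 to 22:00, and the 8 h question falls between 00:00 and 06:00. This option covers hours 0 to 4 and bounds the unknown times. It still gives no offset after the infusion stops, so the aim should then refer to numbness during the infusion and not to its duration.

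Neither option affects the pharmacokinetic data.
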